- m. For WOCBP. Perform serum pregnancy test at Screening. Perform urine pregnancy test prior to dosing at visits on Week 0, Week 2 through Week 24, Follow-up, and Early Termination/Discontinuation (if applicable).
- n. PK sample collected with participants in a fasted state ([Section 5.3.2](#)) at trough (prior to dosing with study intervention) and 2 to 4 hours after administration.
- o. Do not perform assessment/procedure at Day 169 for participants who continued scheduled visits after stopping study intervention and completed Early Termination/Discontinuation assessments/procedures.
- p. ADA samples to be collected prior to dosing with study intervention.
- q. If not collected on the designated collection day, collect at the next available time point when biospecimens are being collected in conjunction with a participant visit.
- r. Assessment to be performed, following ≥4-hour fast, at site (as part of site visit) or separate visit(s) to Imaging facility (see [Section 5.3.2](#)).
- s. Attempts to be made to stay within ±2-hour window of the time when MRI-PDFF was performed at Screening.
- t. Dispense study intervention only to participants assigned to Q2W regimen for home dosing.
- u. For each site visit, perform all indicated procedures and assessments prior to participant self-injection (or caregiver administering injection).
- v. Dosing at home for participants in the Q2W regimens will occur on Weeks 10, 14, 18, and 22; the window for each scheduled dosing day is ±2 days. Study intervention will be dispensed at the prior visit for these doses.

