#### **2.2.4.1. Clinical Pharmacokinetics**

Concentrations of total full-length oligonucleotide in plasma, including the parent compound vupanorsen, its full-length oligonucleotide metabolites with 1, 2, and/or 3 GalNAc sugar deletions and unconjugated vupanorsen, were quantitated as they are all potentially pharmacologically active. For simplicity, vupanorsen concentration refers to all full length oligonucleotides in the context of PK.

In the Phase 1 study, following single-dose or multiple-dose SC administration, vupanorsen was absorbed rapidly into the systemic circulation, with median  $T_{max}$  ranging from 1 to 8 hours. After reaching  $C_{max}$ , plasma concentrations of vupanorsen declined in a multi-phasic fashion with a rapid disposition phase, followed by a slower elimination phase with mean terminal elimination half-life of 3 to 5 weeks.  $C_{max}$  and AUC increased approximately dose proportionally from 20 mg to 120 mg after a single SC dose, and from 10 mg to 60 mg after

single and multiple weekly SC doses. No accumulation was observed based on  $C_{\max}$  and AUC after weekly doses. Plasma trough concentrations indicated that steady-state was not reached after 6 weeks of weekly dosing, consistent with the observed long half-life of the drug.

Vupanorsen PK profiles were evaluated in a subset of participants in the Phase 2a study. Following 20 mg QW, 40 mg and 80 mg Q4W SC dosing, the observed preliminary vupanorsen PK in the Phase 2a study were consistent with those in the Phase 1 study. Plasma trough concentrations appeared to reach steady-state after 21 weeks of dosing. The presence of ADA showed no apparent impact on  $C_{\max}$  and AUC, but increased plasma trough concentrations based on preliminary analysis.

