**Prior/Concomitant Therapy:**

10. Prior treatment at any time with vupanorsen.
11. Prior treatment with any oligonucleotide (including small interfering ribonucleic acid) within 6 months of Screening or prior treatment with inclisiran within 12 months of Screening.
12. Use of TG lowering medication (eg, Vascepa [icosapent ethyl]), non-prescription dietary supplements (eg, fish oil) or other cholesterol lowering medication (eg, fibric acid derivatives, niacin, PCSK9 inhibitors, bile acid sequestrants, bempedoic acid) 30 days prior to Screening, other than statins and ezetimibe.
13. Use of warfarin or other coumarins, direct thrombin inhibitors, Factor Xa inhibitors, heparins or heparinoids 30 days prior to Screening.

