## **8.9. Immunogenicity Assessments**

Immunogenicity of vupanorsen will be assessed before, during, and after treatment. A listing of individual plasma ADA results (including ADA positive, negative, and unknown status

samples and titers) sorted by treatment group, participant ID, planned visit, and the visit date/time will be reported. The incidence (number) and incidence rate (percent) of ADA positive, negative and unknown participants will be summarized by treatment group and planned visit and for the overall study. The ADA positive participants will be further subcategorized into TEADA if the baseline ADA is negative. The incidence and incidence rate of TEADA will be summarized by treatment group and planned visit and for the overall study.

Potential relationships of immunogenicity with selected efficacy, safety, and PK concentrations may be evaluated.

Blood samples of approximately 6 mL will be collected in K2 EDTA tubes, to provide a minimum of 3 mL plasma for determination of ADA as specified in the [SoA](#). Instructions for the collection and handling of biological samples will be provided in the laboratory manual or by the sponsor. The actual date and time (24-hour clock time) of each sample will be recorded.

Samples collected for determination of ADA may also be used for additional characterization of the immune response or for other internal exploratory purposes. These data will be used for internal exploratory purposes.

Samples will be analyzed using a validated analytical method in compliance with applicable SOPs. Samples determined to be positive for ADA may be further characterized.

The immunogenicity samples must be processed and shipped as indicated in the instructions provided to the investigator site to maintain sample integrity. Any deviations from the immunogenicity sample handling procedure (eg, sample collection and processing steps, interim storage, or shipping conditions), including any actions taken, must be documented and reported to the sponsor. On a case-by-case basis, the sponsor may make a determination as to whether sample integrity has been compromised.

No immunogenicity data will be provided to study sites, blinded personnel, or the study team until the study has been unblinded.

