### **6.3. Other Endpoint(s)**

#### **6.3.1. Safety Endpoints**

The following will be summarized according to [Section 5.2](#), using the safety analysis set defined in [Section 4.2](#).

- Incidence of treatment-emergent SAEs and AEs throughout the study.
- Incidence of AESI.
- Categorical summaries of clinical laboratory abnormalities:
  - ALT/AST abnormalities:
    - Value  $\geq 3$  x ULN;
    - Value  $\geq 5$  x ULN;
    - Value  $\geq 8$  x ULN.
  - Percent reduction from baseline in eGFR  $\geq 40\%$ .
  - Platelet abnormality:
    - Confirmed platelet counts  $< 100,000$ ;

- Confirmed platelet counts <75,000;
- Confirmed platelet counts <50,000.
- Platelet count changes:
  - Percent reduction from baseline in platelet counts  $\geq 30\%$ ;
  - Percent reduction from baseline in platelet counts  $\geq 50\%$ .
- UACR;
- ADA.

*Immunogenicity of vupanorsen will be assessed before, during, and after treatment. A listing of individual plasma ADA results (including ADA positive, negative, and unknown status samples and titers) sorted by treatment group, participant ID, planned visit, and the visit date/time will be reported. The incidence (number) and incidence rate (percent) of ADA positive, negative and unknown participants will be summarized by treatment group and planned visit and for the overall study. The ADA positive (ADA+) participants will be further subcategorized into TEADA if the baseline ADA is negative. The incidence and incidence rate of TEADA will be summarized by treatment group and planned visit and for the overall study.*

- ECG (Section 9.4.5.1. of the protocol);
- Vital signs (BP and pulse rate).

The following will be summarized and (percent) change from baseline will be analyzed according to [Section 5.2](#), using the safety analysis set:

- AST;
- ALT;
- Platelet counts;
- eGFR;
- Hepatic fat fraction;
- UACR.

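### TEADA as defined excludes participants who are ADA positive at baseline and whose titer rises on vupanorsen, so the treatment-emergent count by arm omits any boosted cases

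*Protocol*

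**What the plan says.** Immunogenicity is part of the safety objective, and ADA is a listed safety endpoint (Protocol Section 3; SAP 2.1 and 3.5).

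- **Definition.** Protocol 8.9: "The ADA positive participants will be further subcategorized into TEADA if the baseline ADA is negative". SAP 6.3.1 has the same rule: "The ADA positive (ADA+) participants will be further subcategorized into TEADA if the baseline ADA is negative". Neither document has a treatment-boosted category, a titer-rise threshold or any other route into TEADA.
- **TEADA reporting.** Protocol 8.9: "The incidence and incidence rate of TEADA will be summarized by treatment group and planned visit and for the overall study". The SAP matches. The denominator is not stated.
- **ADA status reporting.** Counts and percentages of ADA positive, "negative and unknown participants will be summarized by treatment group and planned visit and for the overall study" (Protocol 8.9).
- **Titers.** SAP 6.3.1 plans "A listing of individual plasma ADA results (including ADA positive, negative, and unknown status samples and titers) sorted by treatment group". No summary of titers by arm is planned.
- **Sampling.** The Schedule of Activities has ADA samples on Day 1, at Weeks 12, 16, 20 and 24, at follow-up and at early termination. For the scheduled visits from Day 1 to Week 24 its footnote reads "ADA samples to be collected prior to dosing with study intervention". A baseline status and a baseline titer can therefore be known.
- **Prior exposure.** Anyone ever given vupanorsen is excluded. For other products the exclusion is time-limited: "Prior treatment with any oligonucleotide (including small interfering ribonucleic acid) within 6 months of Screening", with 12 months for inclisiran (Protocol 5.2).

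**The concern.** A drug can provoke antibodies in someone who had none, or it can raise a response that was already there. Both arise on treatment. The rule captures only the first, although the label TEADA suggests both. A participant with a low titer on Day 1 and a much higher one at Week 24 is classified like a participant whose pre-existing antibody never moved.

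The trial is meant to support dose selection, and the TEADA table is its only summary of treatment-emergent antibodies by dose. If boosted responses occur, that table does not show them, and no other planned table separates them out. The data needed to do so are already being collected.

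**Working it through.** The documents state no ADA or TEADA figure, so there is nothing to reproduce. The check is of the rule's logic, followed by an illustration of size.

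**1. Where each kind of participant appears**

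| Day 1 ADA | On treatment | TEADA table | ADA-positive table | Titer listing |
|---|---|---|---|---|
| Negative | Becomes positive (induced) | Yes | Yes | Yes |
| Positive | Titer rises (boosted) | No | Yes | Yes |
| Positive | Titer unchanged | No | Yes | Yes |

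The second and third rows are identical. Subtracting TEADA from all ADA positives leaves the baseline positives (plus any with unknown baseline status), but it cannot divide them into boosted and unchanged. Only the participant-level listing can do that, and the plan gives no rule for reading it.

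**2. Effect on the count**

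Let N be the arm size, b the share ADA positive at baseline, and q the share of those whose titer rises on drug.

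- Cases left out = N × b × q. This is zero or positive, never negative.

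**3. Effect on the rate, if all participants are the denominator**

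- Shortfall = b × q.
- One case in a 20-participant arm: 1/20 = 5 percentage points. In a 40-participant arm: 1/40 = 2.5 points.

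The documents give neither b nor q. The values below are assumptions chosen to show a range. Shortfall in percentage points:

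| b | q = 25% | q = 50% | q = 100% |
|---|---|---|---|
| 0% | 0 | 0 | 0 |
| 2% | 0.5 | 1.0 | 2.0 |
| 5% | 1.25 | 2.5 | 5.0 |
| 10% | 2.5 | 5.0 | 10.0 |

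At the extreme (b = 10%, q = 100%) this is 20 × 0.10 = 2 participants in a 20-participant arm and 40 × 0.10 = 4 in a 40-participant arm. At b = 2% and q = 25% it is 20 × 0.02 × 0.25 = 0.1 and 40 × 0.02 × 0.25 = 0.2 participants.

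**4. Effect on the rate, if baseline negatives are the denominator**

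Let i be the induced rate among baseline negatives. The rule then reports i, while the combined rate over all participants is (1 − b) × i + b × q. The difference, combined minus reported, is b × (q − i), which can take either sign. With i = 20% and b = 5%:

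- q = 50%: combined = 0.95 × 20% + 0.05 × 50% = 21.5%, against 20% reported.
- q = 10%: combined = 0.95 × 20% + 0.05 × 10% = 19.5%, against 20% reported.

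The understatement of the count is therefore certain whenever a boosted case exists. The understatement of the rate depends on a denominator that neither document states.

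**5. Which analyses use TEADA**

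- PK concentrations: stratified by immunogenicity status (Protocol 8.5), which SAP 6.3.2 specifies as ADA status.
- Efficacy subgroup: ADA positive against negative (SAP 6.4).
- TEADA: its own incidence table only (Protocol 8.9; SAP 6.3.1).

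**The case against.** The strongest reply is that this is a choice of definition. The two documents agree, the rule is clear and reproducible, and the incidence of new antibody in baseline negatives is a legitimate quantity. Nothing in either document requires TEADA to include boosted responses, and in an exploratory study no decision rule depends on it. This explains why the point is small. It does not explain why a treatment-emergent label should omit one kind of treatment-driven response when the data to include it are at hand.

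Four stronger readings are tempting, and the documents support none of them:

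- **Boosted participants disappear from the immunogenicity results.** They do not. They are counted as ADA positive by arm, by visit and overall, and their titers are listed. The omission is from TEADA only.
- **The omission distorts the exposure or efficacy results.** The planned PK and efficacy analyses use ADA status, not TEADA. The Phase 2a finding in Protocol 2.2.4.1 is also mixed: "The presence of ADA showed no apparent impact on" Cmax and AUC, with higher trough concentrations on a preliminary analysis. It says nothing about boosted antibodies in particular. Protocol 8.9 allows for looking at relationships between immunogenicity and other outcomes, but only as an option.
- **Baseline positivity is to be expected.** The exclusions leave room for earlier exposure to other oligonucleotides, but antibody to vupanorsen from that source would need cross-reactivity, which neither document reports. A rule conditioned on a negative baseline is not evidence that positives are anticipated.
- **A definite number of participants is affected.** Taking 2% to 10% of the 220 planned vupanorsen participants (260 − 40) gives 4.4 to 22. That counts all assumed baseline positives, before asking how many are boosted, and the percentages are themselves assumed.

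**Conclusion.** The point holds as a minor gap in a definition. Under the written rule, a participant who is ADA positive on Day 1 cannot enter the only planned treatment-emergent ADA summary, whatever the titer does afterwards. The number of treatment-emergent cases by arm is too low by exactly the number of boosted participants. That number is not given and could be zero. If it is not zero, each case is worth 5 points in a 20-participant arm and 2.5 points in a 40-participant arm, on an all-participant denominator.

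A reader might infer that the TEADA rate is necessarily biased low. That does not follow while the denominator is unstated: among baseline negatives, the rule gives a proper induced rate. No primary, secondary, PK or planned subgroup analysis is affected.

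**What to change.** In Protocol 8.9 and SAP 6.3.1:

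1. Define TEADA as either treatment-induced (baseline negative, any post-baseline positive) or treatment-boosted (baseline positive, with a post-baseline titer above a stated multiple of the baseline titer).
2. Fix that multiple from the assay's variability before unblinding. Chosen after titers have been seen by arm, it would be post hoc.
3. Tabulate induced, boosted and unchanged pre-existing positives separately by arm, and state the denominator for each.
4. State how participants with unknown or missing baseline ADA are classified, which the current rule leaves open.

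The cost is one derived flag, some SAP wording and a matching edit to the protocol. No new samples or assays are needed. Protocol Section 9 lets the SAP modify what the protocol outlines and calls for a protocol amendment only for major changes to the primary endpoint definition or analysis, so the SAP change need not wait for one. The downside is a TEADA incidence that may look slightly less favourable.

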#### **8.10. Health Economics**

Health economics/medical resource utilization and health economics parameters are not evaluated in this study.

### **9. STATISTICAL CONSIDERATIONS**

Detailed methodology for summary and statistical analyses of the data collected in this study is outlined here and further detailed in the SAP, which will be maintained by the sponsor. The SAP may modify what is outlined in the protocol where appropriate; however, any major modifications of the primary endpoint definitions or their analyses will also be reflected in a protocol amendment.

## 9.1. Estimands and Statistical Hypotheses

### 9.1.1. Estimands

The primary estimand of this study will follow the hypothetical estimand approach to estimate the effect of treatment under the hypothetical condition that all participants maintained their randomized treatment through Week 24. This estimand is meant to estimate the pharmacological effect of the drug when taken as directed. It includes the following 4 attributes:

- Population: Participants with dyslipidemia taking a statin who meet the inclusion/exclusion criteria.
- Variable: The percent change from baseline in non-HDL-C at Week 24.
- Intercurrent event: All off-treatment data (ie, occurring at least 1 dosing interval after discontinuation of treatment), or data collected post treatment of severe hypertriglyceridemia (ie, change in statin dose or addition of TG lowering therapy; [Section 8.2.7](#)), if collected, will be excluded from analysis.
- Population-level summary: Difference of variable means between vupanorsen and placebo.

### 9.2. Sample Size Determination

Assuming a common standard deviation of 17.5% (observed in the Month 6 data of the Phase 2a proof-of-concept and dose-ranging study) for the percent change from baseline in non-HDL-C at Week 24 and a treatment discontinuation rate of 15%, 20 participants per arm will correspond to a 95% CI of point estimate  $\pm 11.76\%$  for the difference of treatment effect (versus placebo). These parameters correspond to a power of 91.5% using a 2-sided alpha of 0.05, to detect a difference of -20%, without adjustment for multiple comparison to placebo.

A permutation block schedule will be used in enrollment within each arm, including vupanorsen and matching placebo. If enrollment is stopped for the 160 mg Q2W arm (see [Section 4.1](#)), the corresponding matching placebo enrollment will also be stopped.

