**Table 1. Dosing Plan**

Treatment Arm	Total Monthly Dose	Injection Regimen	Number of Participants
Placebo	0 mg	Single or double injection Q2W or Q4W	40
80 mg Q4W	80 mg	Single injection Q4W	20
60 mg Q2W	120 mg	Single injection Q2W	20
120 mg Q4W	120 mg	Double injection Q4W	20
80 mg Q2W	160 mg	Single injection Q2W	40
160 mg Q4W	160 mg	Double injection Q4W	40

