Since administration of 160 mg Q2W (total monthly dose of 320 mg) has not been studied previously, enrollment in this arm will be capped after 10 participants. Following unblinded data review by the E-DMC as described in the E-DMC charter, enrollment in this treatment arm may be re-opened for the remaining 30 participants or be stopped based on recommendation by the E-DMC. Separately, an interim analysis is planned and will also be reviewed by the E-DMC. The interim analysis will take place approximately 16 weeks after 50% of the planned participants (ie, approximately 110 participants), with exception of the 160 mg Q2W group, are randomized.

Efficacy and safety analyses will occur when all participants either complete 24 weeks of study participation or discontinue study participation. Additional summarizing of follow-up safety data will occur after the 12-week post-dose follow-up visit.

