#### 5.1. Hypotheses and Decision Rules

The null hypothesis for the primary endpoint is:

$H_0$ : There is no difference in mean percent change from baseline in non-HDL-C at Week 24 between vupanorsen and placebo.

The study objective is treatment effect estimation and dose selection and therefore no formal decision rules for inferential purposes are planned. Each vupanorsen treatment group will be compared to the pooled placebo group, ie, placebo-adjusted LS-mean treatment effect for each dose will be reported along with 95% CI and p-value without adjustment for multiple comparisons to placebo.

The Mixed Model Repeated Measurements (MMRM) will be used as the primary statistical method to estimate the difference of treatment effect between each dose of vupanorsen versus placebo at Week 24. Statistical inference including effect size, p-value, 95% CI will be presented for primary and secondary endpoints respectively, with no adjustment for multiplicity.

Although an interim analysis will occur at Week 16, no formal hypothesis testing nor statistical inference will be conducted.

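### The stated precision (±11.76%) and power (91.5%) against placebo describe a 20 v 20 comparison that the trial does not contain

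*Protocol*

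**What the plan says.** Protocol Section 9.2 sets out its planning inputs ("Assuming a common standard deviation of 17.5"%, with 15% discontinuing treatment) and reports that "20 participants per arm will correspond to a 95% CI of point estimate" ±11.76% for the difference from placebo. It continues: "These parameters correspond to a power of 91.5% using a 2-sided alpha of 0.05, to detect a difference of -20"%. No adjustment is made for the several comparisons with placebo. The synopsis repeats the same figures under Statistical Methods. Neither place gives a figure for any other arm size.

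Protocol Table 1 (and SAP Table 1) has a single placebo row of 40 participants, whose injection regimen is "Single or double injection Q2W or Q4W". Three vupanorsen arms have 20 participants (80 mg Q4W, 60 mg Q2W, 120 mg Q4W). Four have 40 (80 mg Q2W, 160 mg Q4W, 120 mg Q2W, 160 mg Q2W).

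SAP Section 5.1 names the comparator: "Each vupanorsen treatment group will be compared to the pooled placebo group".

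The 160 mg Q2W arm is capped at 10 participants pending E-DMC review. Protocol Section 4.1 says that enrollment in it "may be re-opened for the remaining 30 participants or be stopped based on recommendation by the E-DMC". If it stops, Section 9.2 adds that "the corresponding matching placebo enrollment will also be stopped".

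**The concern.** The sample-size statement and the design describe different comparisons. Every planned placebo contrast is 20 v 40 or 40 v 40, whereas the statement reads as 20 v 20. It also passes over the fact that four arms are twice the size of the other three, and so does not show what precision the extra participants buy.

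SAP Section 5.1 gives the purpose of the study as effect estimation and dose selection, with no formal decision rules. In such a trial the planned confidence-interval width is the main justification for the arm sizes, and Section 9.2 is the only place where it appears. As written, the section does not state the planned precision of any comparison that will be made.

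A second gap is linked to this one. If the 160 mg Q2W arm stops, its matching placebo stops too, but the documents do not say how many placebo participants would then remain. The comparator size in that case is unknown.

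**Working it through.** **Inputs**

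- SD 17.5%, discontinuation 15%, two-sided alpha 0.05, difference 20%: Protocol Section 9.2.
- Arm sizes 20 and 40, placebo 40: Protocol Table 1.
- Comparator is pooled placebo: SAP Section 5.1.
- Evaluable numbers: 20 × 0.85 = 17 and 40 × 0.85 = 34.

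**Formulas** (unadjusted two-sample normal approximation)

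- SE = 17.5 × √(1/n₁ + 1/n₂)
- Half-width = 1.96 × SE
- Power = Φ(20/SE − 1.96)

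**Step 1: reproduce the plan's figures.** With 17 v 17, SE = 17.5 × √(2/17) = 6.002. The half-width is 1.96 × 6.002 = 11.76, and power is Φ(3.332 − 1.96) = Φ(1.372) = 0.915. Both match. No other layout tried gives both figures: 20 v 20 without discontinuation gives 10.85 and 95.1%, 20 v 40 without discontinuation gives 9.39 and 98.7%, and 17 v 17 with t quantiles gives 12.23 and 89.8%. The stated figures therefore assume 20 randomized to placebo.

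**Step 2: apply the same method to the planned contrasts.**

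| Contrast (randomized) | Evaluable | SE | Half-width | Power |
|---|---|---|---|---|
| As stated, 20 v 20 | 17 v 17 | 6.002 | 11.76 | 91.5% |
| Three smaller arms, 20 v 40 | 17 v 34 | 5.198 | 10.19 | 97.0% |
| Four larger arms, 40 v 40 | 34 v 34 | 4.244 | 8.32 | 99.7% |

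Ratios of half-widths: 11.76/10.19 = 1.15 and 11.76/8.32 = 1.41. The stated half-width is 15% too wide for the smaller arms and 41% too wide for the larger ones.

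With t quantiles and noncentral t power, the planned contrasts give 10.45 (96.5%) and 8.47 (99.6%), so the conclusion does not depend on the approximation.

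**Step 3: the 160 mg Q2W arm stopped at 10 (assumption).** The documents do not say how placebo is split across regimens. Suppose it is matched in proportion to the 220 active places. The share of this arm is then 40 × 40/220 = 7.3, and the share of its 30 unfilled places is 30 × 40/220 = 5.5. Placebo would end at about 33 to 35 randomized, or 28 to 29 evaluable in whole numbers. The stopped arm would have 8 or 9 evaluable (10 × 0.85 = 8.5).

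| Contrast under this assumption | Evaluable | Half-width | Power |
|---|---|---|---|
| Stopped arm, least favorable | 8 v 28 | 13.75 | 81.4% |
| Stopped arm, most favorable | 9 v 29 | 13.09 | 85.0% |
| 20-participant arms | 17 v 28 to 29 | 10.55 to 10.48 | about 96% |
| 40-participant arms | 34 v 28 to 29 | 8.75 to 8.67 | above 99% |

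For the stopped arm, the t versions run from ±13.5 to ±14.3%, with power 79 to 83%.

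**The case against.** The strongest defense is that nothing has been miscalculated. The section states its premise of 20 per arm, and the figures are correct for it. They also act as a safe bound. For any arm of at least 20 participants, and any placebo total of at least 20, the true half-width is no wider and the power no lower than stated. The study is exploratory, no decision rule uses the figures, and a reader with Table 1 and the formula can work out the rest. Moreover, figures quoted against 40 placebo would be slightly optimistic if matching placebo were stopped early, and an arm halted at 10 lies outside the stated premise.

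Much of this stands. The arithmetic is right, the mismatch is conservative for fully enrolled arms, and the stopped-arm figures rest on an assumed placebo allocation.

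It does not rescue the statement. The section presents its figures as the precision and power against placebo. It does not call them a minimum or say that they ignore half of the placebo group. They cannot be read as referring to regimen-specific placebo either: SAP Section 5.1 pools placebo, and 40 participants spread over seven active regimens could not supply 20 to each. That readers could derive the correct figures is no reason to print figures for another layout. The worry about a reduced placebo group is met by naming the denominator.

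**Conclusion.** The concern holds. The figures in Section 9.2 and the synopsis are correctly computed for a 20 v 20 comparison, and none is planned. With 40 pooled placebo, SD 17.5%, 15% discontinuation and the normal approximation, the planned figures are ±10.2% (power 97%) for the three 20-participant arms and ±8.3% (power above 99%) for the four 40-participant arms.

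The consequence is limited: the error understates what the design delivers, and no fully enrolled arm is underpowered. Only a 160 mg Q2W arm stopped at its cap would fall short of the stated figures. Its size there (±13.1 to 13.8%, power 81 to 85%) depends on the assumed 33 to 35 placebo participants.

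All these numbers are unadjusted planning approximations, like the protocol's own. They are not the precision of the baseline-adjusted MMRM.

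**What to change.** In Protocol Section 9.2 and the synopsis, keep the SD, the discontinuation rate and the method, and replace the precision and power statement with:

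> Versus 40 pooled placebo: ±10.2% (power 97%) for 20-participant arms and ±8.3% (power >99%) for 40-participant arms.

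Optionally, add a separate sentence for the case in which the 160 mg Q2W arm stops at 10. It should first say how many placebo participants remain once matching placebo stops, and then give the half-width and power of that arm and of the others against that number. The contingency figures above illustrate an assumed allocation and should not be inserted.

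The cost is a wording change in two places in the protocol. Sample size, randomization and analysis are unaffected.
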